that the therapeutic benefits have been sustained over time on average, although two subjects experienced a relapse in PTSD symptoms [2]. The sponsor also supported a randomized, double-blind pilot study in 12 subjects with chronic, treatment-resistant PTSD in Switzerland with three experimental sessions. The study results suggested a trend toward significant improvement in subjects receiving full dose MDMA, when compared to 25 mg active placebo MDMA at two-month follow-up. The improvement continued to increase during the 12-month follow-up [3]. In addition, the sponsor supported an initial pilot study with two experimental sessions comparing full dose to 25 mg active placebo MDMA in Israel that enrolled five subjects, with no drug-related Serious Adverse Events (SAEs). Subjects reported benefits that were not reflected in CAPS scores, leading to termination of the study for additional training of the Israeli therapists and research team. Most recently, in the U.S., MAPS has commenced a follow-up to its initial U.S. trial with a PTSD relapse study, along with a second Phase 2 trial, specifically treating U.S. military veterans.

As of March 2014, MDMA has been administered to more than 960 research subjects, in both Phase 1 and Phase 2 studies, without any occurrences of unexpected drug-related SAEs [1, 3, 47, 68, 72-95].

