2.3 Protocol Purpose

This Phase 2 pilot study is a randomized, double-blind, dose response study in 23 subjects comparing the effects of two active doses and a comparator dose of MDMA as an adjunct to manualized psychotherapy. In Stage 1 the study will assess two different active doses (100 mg and 125 mg) and one comparator dose (40 mg) of MDMA, an optional supplemental dose that is half of the assigned dose may be offered to all subjects 1.5 to 2.5 hours after the initial dose. Nine subjects will be randomized to active dose group 1, nine subjects to active dose group 2, and five subjects will be randomized to receive the comparator dose. Stage 1 of the study will consist of two blinded experimental sessions and one open-label experimental session of manualized MDMA-assisted psychotherapy, each lasting six to eight hours and scheduled three to five weeks apart, within a moderate course of non-drug psychotherapy.

The study will be unblinded one month after the second experimental session in Stage 1, after completion of outcome measures, which constitutes the primary endpoint assessment. After unblinding, subjects who received active dose 1 (125 mg MDMA with optional supplemental half dose) during the first two sessions will receive the same active

dose during the open-label third experimental session. Subjects who received active dose 2 (100 mg MDMA with optional supplemental half dose) during the first two sessions will be able to choose, in consultation with the therapist, to either continue to receive active dose 2 during the third session or to increase their dose to active dose 1. The benefit of three versus two active dose sessions will be assessed.

Subjects who received the comparator dose during Stage 1 will have the opportunity to cross over to Stage 2 with three open-label experimental sessions at equivalent time points to Stage 1. Stage 2 will be used to explore the optimal therapeutic dose of MDMA using a clinical titration dosing strategy. The active dose 2 will be administered during the first experimental session and the therapists will choose one of the two active doses of MDMA for the second and third experimental sessions, with an optional supplemental half-dose.

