Upon enrollment, subjects will be randomly assigned to receive either active dose 1 (nine subjects), active dose 2 of MDMA (nine subjects), or comparator dose (five subjects). In Stage 1, subjects will meet with their therapist team for three preparatory sessions and two blinded experimental psychotherapy sessions of MDMA-assisted psychotherapy. After each experimental session, subjects will stay overnight at the site and complete an integrative psychotherapy session the next day, followed by daily telephone calls for the next seven days and two additional integrative sessions. One month after the second experimental session, the primary endpoint assessment will take place, after which the blind will be broken. Subjects who receive one of the active doses will receive a third open-label experimental session with similar procedures. Subjects who receive the active dose 2 during the first two experimental sessions will be given the option to increase their dose in the third experimental session to match the active dose 1 condition. Subjects who receive the comparator dose will be offered the option to continue to the open-label Stage 2 unless they meet any exclusion criteria for study participation. Stage 2 will be used to explore the optimal therapeutic dose of MDMA using a clinical titration dosing strategy. After a single preparatory session, active dose 2 will be administered at the first session and the therapists will choose one of the two active doses of MDMA for the second and third experimental sessions, with an optional supplemental half dose at each of three experimental sessions at time points equivalent to those in Stage 1 (See Time and Events Table).

[figure not shown]
A blinded IR will administer outcome measures. The IR will assess PTSD symptoms with the CAPS, quality of life with the GAF, symptoms of depression with the BDI-II, sleep quality with the PSQI, posttraumatic growth with the PTGI (in reference to the start of the study), and dissociation with the DES-II. The subjects will complete the PDS, a self-report measure of their PTSD symptoms, to provide correlations with measures administered by the IR. A blinded IR will also assess cognitive function with the Paced Auditory Serial Addition Test (PASAT) and the Repeatable Battery for the Assessment

of Neuropsychological Status (RBANS) at baseline and the primary endpoint by condition, and end of Stage 1/end of Stage 2 for maximal exposure.

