For exploratory purposes, the sponsor will examine individual PDS, BDI-II, GAF, PSQI, PTGI, and DES-II scores at baseline and the primary endpoint in each active dose and comparator dose conditions. Analysis of variance, or nonparametric analysis if assumptions are not met, will be used to compare the dose conditions for change in BDI-II, PTGI, PSQI, GAF, and DES-II scores separately. If scores cannot be examined sufficiently in this model, then analyses will compare available data through the use of difference scores.

Changes in CAPS from the primary/secondary endpoint to the two-month follow-up in Stage 1/Stage 2 will be compared for a within-subject analysis with p value set at 0.05 to see whether a third session with an active dose produces further decline in symptoms. Stage 2 data will only be combined with open label Stage 1 data for this analysis, if data is equivalent between stages based on confidence intervals. Subjects who receive active

dose 1 in the third experimental session may be compared to subjects who receive active dose 2 for exploratory purposes if at least three subjects are in either group. If less than three subjects from the 100mg group select active dose 2, then analyses will be conducted with and without these subjects to determine the effect of a third session with active dose 1. The sponsor will perform an exploratory within-subject analysis of crossover participants in Stage 2.

A repeated measures analysis of variance (ANOVA) will be performed upon PDS scores at baseline, after each experimental session, and at the end of Stage 1, with p value set at 0.05. Condition will serve as a between-subjects factor. Results of ANOVA analysis will be used to examine the effects of each experimental session on self-reported PTSD symptom severity. PDS and CAPS scores will be correlated via Pearson's product moment correlation at baseline and the primary endpoint to provide a comparison of a self-report measure with a clinician-administered measure of PTSD symptoms.

The sponsor will compute descriptive statistics for SOCQ scores from after each MDMA-assisted psychotherapy session, and average SOCQ scores for blinded experimental sessions will be compared between conditions. The data will be explored for effects of condition on domain scores in the SOCQ.

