9.0 Analyses

In general, nominal variables will be described in terms of frequencies and percentages and analyzed using chi square analysis. Ordinal and non-normal continuous variables will be described using sample median and range, and analyzed by non-parametric statistical tests, and approximately normal variables will be described using sample mean and standard deviations and analyzed by parametric statistical tests. All statistical tests will be two-sided and a difference resulting in a p-value of less than or equal to 0.05 will be considered statistically significant. All p-values will be rounded to and displayed in four decimals. If a p-value less than 0.0001 occurs it will be shown in tables as <0.0001. For any analysis that is called out as parametric, e.g. t-test, the parametric assumptions will be examined. If necessary, nonparametric analyses will be utilized, e.g. Wilcoxon rank-sum test.

Clinical data will be presented in tabular format. Data not subject to analysis according to this plan will not appear in any tables or graphs, but will be included in the data listings. Analyses will be carried out with SAS Version 9.3 or higher. Selected results may be presented graphically using standard graphical software.

Post-hoc exploratory analyses not identified in this SAP may be performed to further examine the study data. These analyses will be clearly identified as such in the final clinical study report.

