9.9.2.1 Secondary Efficacy Analyses at Secondary Endpoints

Assess 3 vs. 2 experimental MDMA sessions

For the CAPS, the absolute changes in the measure from the primary endpoint to end of Stage 1 for the 100 and 125 mg groups will be compared with t-tests. In the crossover subjects (40 mg) the absolute changes in the measures from the secondary (visit 27) endpoint to end of Stage 2 (visit 32) will be compared with t-tests.

Crossover Subject Analyses

CAPS data from subjects assigned to the 40 mg group in Stage 1, i.e. ‘crossover population,’ will be analyzed by t-tests on difference scores from primary endpoint (visit 12) in Stage 1 to secondary endpoint in Stage 2 (visit 27). Additionally, the following measures’ total scores will be analyzed in this same fashion: CAPS, PTGI, BDI-II, GAF, PSQI, DES-II, PDS.

Long-term Follow-up

For the CAPS, PDS, PTGI, BDI-II, GAF, PSQI, and DES-II, the absolute changes in the measures from baseline to the long-term follow-up visit (one year post final experimental year) will be compared with t-tests. The absolute changes in the measures from long-term follow-up to End of Stage 1 (visit 17, 100 mg and 125 mg) or long-term follow-up compared to End of Stage 2 (visit 32, 40 mg) will be compared with t-tests.

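### The within-subject CAPS test after the third session shows whether scores changed, not whether three active sessions are better than two

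*Protocol*

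**What the plan says.** Protocol Section 2.3 promises: "The benefit of three versus two active dose sessions will be assessed". Section 12.0 carries this out on CAPS change from the primary endpoint (V12) to the end of Stage 1 (V17), and from the secondary endpoint (V27) to the end of Stage 2 (V32), in a "within-subject analysis with p value set at 0.05 to see whether a third session with an active dose produces further decline in symptoms".

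SAP Section 9.9.2.1 heads the analysis "Assess 3 vs. 2 experimental MDMA sessions". For Stage 1 it plans t-tests, in these words: "absolute changes in the measure from the primary endpoint to end of Stage 1 for the 100 and 125 mg groups will be compared". The V27 to V32 changes in crossover subjects are handled the same way. It does not say whether the Stage 1 t-tests are paired within a dose group or run between the two groups. SAP Section 9.0 sets the criterion: "All statistical tests will be two-sided", and "a p-value of less than or equal to 0.05 will be considered statistically significant".

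On who receives the session, Protocol Section 4.0 states: "Subjects who receive one of the active doses will receive a third open-label experimental session with similar procedures". Under Section 5.2.7, comparator subjects have no third session in Stage 1 and are offered Stage 2 instead.

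**The concern.** The question is comparative and causal: does a third active session lower CAPS beyond what two sessions would have achieved by the same date? A paired test on the V12 to V17 change has zero mean change as its null. That is also the null for the session question only if CAPS would have stayed flat without the session, and nobody in the trial is observed under that condition.

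Three things besides the session package differ between the two visits. At least two months pass. V12 falls one month after a dose and V17 two months after one. In Stage 1, subjects learn their assignment at V12, so the whole interval is open-label.

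The objectives say these analyses are meant to inform protocol design. A significant decline could therefore feed into the number of sessions in later trials as if it had been a controlled comparison.

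**Working it through.** **1. The plan's own figure.** The documents give no power or error calculation for this test. The only power statement is for the primary comparison (Protocol Section 12.1): 18 versus 5, effect size 0.8, power 0.33. With a noncentral t, ncp = 0.8 / sqrt(1/18 + 1/5) = 0.8 / 0.5055 = 1.58 on 21 df, and two-sided power at 0.05 is 0.327. The stated figure reproduces, but it has no bearing on the third-session test.

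**2. Is there a two-session control?**
- Active-dose subjects: all are assigned session 3 (Protocol 4.0 and 5.2.7).
- Comparator subjects: two 40 mg sessions, then the offer of Stage 2. They are not a two-active-session group over V12 to V17.
- Stage 2 subjects: the schedule gives all of them a third session between V27 and V32.

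No group qualifies.

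**3. Does another planned analysis fill the gap?**
- 125 mg versus 100 mg at session 3 (Protocol 12.0, SAP 9.9.3) compares doses. So does the SAP 9.9.2.1 t-test if it is read as between groups.
- The equivalence check between stages (Protocol 12.0) only decides whether to pool.
- Correlating perceptions with CAPS change (Protocol 12.0) looks at expectancy, not time.
- The repeated-measures ANOVA of PDS (Protocol 12.0, SAP 9.9.3) has no two-active-session arm.
- The comparison of the two-month with the 12-month follow-up covers a period without dosing, but after three sessions and with psychiatric medication allowed to resume (Protocol 5.2.8).

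None does.

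**4. What the documents say about drift.** In Section 2.2.3, the 12-subject study with three sessions reports: "The improvement continued to increase during the 12-month follow-up". The same section reports that in the first U.S. study benefit was sustained on average at a mean of 41 months, with two relapses. Section 5.1.2 associates that study with two sessions. Neither report describes the few months at issue here.

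**5. Size under assumed drift.** Let dz = mean background change / SD of change, with no third-session effect. The paired t-test has ncp = dz x sqrt(n) on n - 1 df. Sample sizes are 9 + 9 = 18 (Protocol 5.3) and 12 + 9 = 21 (SAP 6.0). The dz values are assumptions.

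| n | critical t | dz = 0 | dz = 0.25 (ncp) | dz = 0.33 (ncp) | dz = 0.5 (ncp) |
|---|---|---|---|---|---|
| 18 | 2.110 | 5% | 17% (1.06) | 26% (1.40) | 52% (2.12) |
| 21 | 2.086 | 5% | 19% (1.15) | 30% (1.51) | 59% (2.29) |
| 9 (one dose group) | 2.306 | 5% | 10% (0.75) | 14% (0.99) | 26% (1.50) |
| 12 (125 mg, SAP) | 2.201 | 5% | 12% (0.87) | 18% (1.14) | 35% (1.73) |
| 5 (Stage 2 alone) | 2.776 | 5% | 7% (0.56) | 9% (0.74) | 14% (1.12) |

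**6. The other direction.** Suppose the third session truly lowers CAPS by 0.5 SD of change while background drift is upward by 0.25 SD. The net change is 0.5 - 0.25 = 0.25 SD. At n = 18 the chance of rejecting falls from 52% to 17%, so a real benefit is usually missed.

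**The case against.** The strongest reply is that zero change is the right null for the literal question of further decline, that the extension is openly described as open-label, and that the objective is listed as exploratory in a pilot meant to estimate effect sizes. All of that is true. But the protocol wording is causal and the SAP heading is comparative, and the SAP lists the test under secondary efficacy. The test supports neither reading.

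Four stronger readings are tempting, and the documents do not support them.
- *A decline is to be expected even if the session adds nothing.* The report of continued improvement comes from a three-session study, while the course in question is the one after two sessions. The other study reports maintenance with two relapses. Even under assumed downward drift of 0.25 to 0.33 SD, most trials of this size would not reject.
- *The extra integrative sessions and telephone calls are confounders.* Protocol 5.2.7 makes them part of the third-session package, so they belong to the treatment being assessed.
- *The CAPS ratings are unblinded.* The independent rater stays blind to condition after V12 (Protocol 5.2.7). What remains is expectancy in the subject, who knows the dose and answers the interview.
- *The false-positive rate is known to be several times 5%.* The drift sizes are assumed, and if the test is run by dose group the inflation at 0.25 SD is only to 10% or 12%.

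**Conclusion.** The point holds as a limit on what may be concluded. The V12 to V17 and V27 to V32 tests show whether CAPS changed in subjects who all had a third session. They cannot show that the session caused the change or that three sessions are better than two. This follows from the design and does not depend on any drift figure.

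The numerical size does depend on one. Under assumed downward drift of 0.25 to 0.5 SD of change and no third-session effect, the paired test on the combined active groups rejects in about 17% to 52% of trials at n = 18 and 19% to 59% at n = 21. Those figures assume approximately normal changes and complete data. Upward drift would bias the test against the session.

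Severity is modest: the objective is exploratory and the primary endpoint is untouched.

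**What to change.** In Protocol Section 12.0 and SAP Section 9.9.2.1:
1. Report mean CAPS change from V12 to V17 and from V27 to V32 as uncontrolled estimates with 95% confidence intervals, described as change after an open-label third session with its associated therapy and the passage of time.
2. Replace the wording about a third session producing decline, and the three-versus-two heading, with wording that matches. Align the promise in Protocol Section 2.3.
3. State that p<=0.05 on these changes will not be taken as evidence that three sessions are better than two.
4. Say in the SAP whether the Stage 1 t-tests are within or between dose groups. If between, label them as a dose comparison.

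It may be tempting to use PDS change from V16 to V17 as a benchmark for drift without dosing. I would not add it: that interval follows session 3, so it is not the course after two sessions, and V16 has no fixed date.

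The cost is wording only, with no new visits or data. The downside is a weaker claim for the third session, which is all that the design can support.

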2.4 Rationale of Dose Selection

This study will compare the effects of psychotherapy sessions assisted by either one of two active doses of MDMA or a comparator dose. The active dose 1 will be 125 mg MDMA followed 1.5 to 2.5 hours later by an optional supplemental dose of 62.5 mg MDMA. The active dose 2 will be 100 mg MDMA followed 1.5 to 2.5 hours later by an optional supplemental dose of 50 mg MDMA. The comparator dose will be 40 mg MDMA followed 1.5 to 2.5 hours later by an optional supplemental dose of 20 mg MDMA. Eighteen of 23 subjects, or 78%, will be assigned to one of the active dose conditions, and five of 23, or 22%, will be assigned to the comparator dose condition. The active dose 1 is equal to the full dose in other MAPS-supported MDMA/PTSD studies.

Subjects in the comparator dose condition during Stage 1 will have the opportunity to cross over to Stage 2. Stage 2 will be used to explore the optimal therapeutic dose using a clinical titration dosing strategy in the second and third Stage 2 sessions allowing for a

choice between two different active doses of MDMA. In Stage 2 subjects will receive an initial dose of 100 mg followed 1.5 to 2.5 hours later by an optional supplemental dose of 50 mg MDMA during the first experimental session. In the second and third session they will receive an initial dose of 100 mg or 125 mg MDMA followed 1.5 to 2.5 hours later by an optional supplemental dose of 50 mg or 62.5 mg, respectively. The decision to titrate the dose in the second and third session will be based on the experience of the first session. If 100 mg MDMA does not seem to be the optimal therapeutic dose based on the first experimental session in Stage 2, the dosage may be increased by an increment of 25 mg in order to achieve the optimal therapeutic dose. The supplemental doses for each experimental session will be half of the initial dose, respectively. The same choice will be provided to Active Dose 2 subjects continuing on to receive a third experimental session in Stage 1 in an open label context.

Table 1. Dose Regimen

Dose	Initial Dose	Optional Supplemental Dose	Min-Max Cumulative Dose	Min-Max Cumulative Dose with Titration
Active Dose 1	125 mg	62.5 mg	125-187.5 mg	N/A
Active Dose 2	100 mg	50 mg	100-150 mg	N/A
Active Dose 2	100 mg	50 mg	100-150 mg	N/A
+ Optional Titration Dose	25 mg	12.5 mg	N/A	125-187.5 mg
Comparator Dose	40 mg	20 mg	40-60 mg	N/A

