9.9.3 Exploratory Analyses

Clinician Administered PTSD Scale-4 (CAPS-4)

- The percentage of subjects who achieve a 30% drop in CAPS-4 global score at the primary endpoint (visit 12) will be an indirect measure of clinical significance. Descriptive statistics will be computed and displayed by Stage 1 treatment groups.
- The percentage of subjects who no longer meet PTSD diagnostic criteria according to the CAPS-4 at the primary endpoint (visit 12) will be an indirect measure of clinical significance. Descriptive statistics will be computed and displayed by Stage 1 treatment groups.

- CAPS-4 Subscale Scores (B, C, D, F) at the primary endpoint (visit 12) will be analyzed in the same manner as the primary analysis of the global score. Descriptive statistics will be computed and displayed by Stage 1 treatment groups.
- Active dose 1 (125mg) and Active dose 2 (100mg) CAPS data at the primary endpoint will be tested for equivalence using confidence intervals. If the two groups are found to be equivalent, then outcomes for the active dose groups will be combined and will be tested for significant differences from the comparator group using difference scores in independent sample t-tests, with p value set at 0.05.
- Comparison of the effect of a third experimental session with either Active dose 1 or Active dose 2 may be conducted if sufficient group sizes are attained, and analyses comparing outcomes at third session may be conducted with and without Active dose 2 participants who elected to take Active dose 1 during the third experimental session.
- Two regression analyses will be conducted using (1) all subjects with a Frequency score of 2 or greater and an Intensity score of 2 or greater on the CAPS Associated Features 29 or 30 at baseline and (2) baseline DES-II total score as baseline covariates to determine whether the dissociative subtype of PTSD is predictive of treatment outcomes.

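### The optional session-3 dose comparison groups subjects by dose received after an unblinded choice, so selection and regression to the mean can produce a difference when the doses do not differ

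*Protocol*

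**What the plan says.** Protocol 2.3 sets the order of events: "The study will be unblinded one month after the second experimental session in Stage 1, after completion of outcome measures". Subjects randomised to 125 mg then receive the same dose in session 3. Those randomised to 100 mg "will be able to choose, in consultation with the therapist, to either continue to receive active dose 2 during the third session" or to move to 125 mg.

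Protocol 2.4 describes the basis of the choice for Stage 2: "The decision to titrate the dose in the second and third session will be based on the experience of the first session". It then extends the option: "The same choice will be provided to Active Dose 2 subjects continuing on to receive a third experimental session in Stage 1".

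Protocol 12.0 takes CAPS change from the primary (or secondary) endpoint to the two-month follow-up as the third-session outcome. In the same paragraph it says that subjects who receive active dose 1 in session 3 "may be compared to subjects who receive active dose 2 for exploratory purposes if at least three subjects are in either group". The sentence after that gives a separate rule for the case where fewer than three 100 mg subjects stay at 100 mg. SAP 9.9.3 carries the idea forward as an option: analyses "may be conducted with and without Active dose 2 participants who elected to take Active dose 1 during the third experimental session".

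SAP 9.9.2.1 separately plans t-tests on CAPS change from the primary endpoint to the end of Stage 1 for the 100 mg and 125 mg groups. It does not say whether those groups are as randomised or as received in session 3.

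**The concern.** In Stage 1 only the 100 mg arm chooses, and it does so just after the visit that supplies the starting value of the outcome. Grouping by dose received gives a 125 mg set made of randomised 125 mg subjects plus switchers, and a 100 mg set made only of those who chose to stay.

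If subjects doing worse are more likely to step up, switchers start high on CAPS and fall on average, while stayers start low and rise on average, whatever the dose does. Change from Visit 12 reads both movements as an advantage of 125 mg. Leaving out the switchers does not help, because the stayers are still the selected, low-scoring part of their arm.

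The stake is the estimate itself. Protocol 3.2 and SAP 4.2 place the effect of the third session among the exploratory analyses that are to inform protocol design. The Visit 12 primary comparison is complete before any choice is made and is not touched.

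**Working it through.** The documents give no figure for this comparison. Their only power figure, 0.33 for 18 v 5 at effect size 0.8 (Protocol 12.1), concerns the pooled active doses against the comparator. A two-sided two-sample t-test at 0.05 reproduces it (0.327), but it has no bearing here.

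**Inputs from the documents.** Allocation is 12 at 125 mg and 9 at 100 mg (SAP 6.0), or 9 and 9 (Protocol 5.3). Grouping is by dose received, and the outcome is change from Visit 12.

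**Assumptions, because the documents are silent.**
- CAPS SD is 25 at both visits.
- The Visit 12 to Visit 17 correlation ρ is 0.6, 0.7 or 0.8. The nearest anchor is the PDS test-retest value of 0.74 (Protocol 5.1.1), which is for another scale.
- Half of the 100 mg arm steps up, according to a latent score with correlation r to Visit 12 CAPS. With r = 1, everyone above the mean steps up and nobody else does.
- There is no dose effect.

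**Closed form.**
- With Visit 12 CAPS z SDs from its mean, expected change relative to the overall mean change is −(1 − ρ) × 25 × z.
- Splitting a normal variable at its mean puts the halves at ±0.798 SD, so stayers average z = −0.798r and switchers z = +0.798r.
- Stayers therefore drift up by B = (1 − ρ) × 25 × 0.798 × r, switchers fall by B, and randomised 125 mg subjects move by 0.
- Switchers excluded: difference = −B.
- Switchers included (4.5 expected among 12 + 4.5 = 16.5): difference = −B × (1 + 4.5/16.5) = −1.273B.

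| ρ | B, r = 1 | Included, r = 1 | Included, r = 0.4 |
|---|---|---|---|
| 0.6 | 0.4 × 25 × 0.798 = 7.98 | −10.2 | −4.1 |
| 0.7 | 0.3 × 25 × 0.798 = 5.99 | −7.6 | −3.0 |
| 0.8 | 0.2 × 25 × 0.798 = 3.99 | −5.1 | −2.0 |

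Negative values favour 125 mg. At r = 0 every entry is 0. At r = −0.4 the last column changes sign and favours 100 mg.

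**Simulation check.** With 20,000 trials per correlation, r = 1 and at least three stayers required, the differences were −10.2/−7.5/−5.1 with switchers and −8.2/−5.9/−4.1 without. By randomised arm they were at most about 0.6 in size, a residue of discarding trials with fewer than three stayers. In a shorter run of the same model (6,000 trials), two-sided type I error was 0.12/0.10/0.08 with switchers and 0.08/0.08/0.07 without. At r = 0.4 it was about 0.06.

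**Is adjustment for Visit 12 CAPS the cure?** Visit 12 CAPS follows two randomised-dose sessions. Suppose 125 mg is 10 points better at Visit 12 and that gap simply persists, with no session-3 dose effect. Unadjusted change by arm is 10 − 10 = 0. The by-arm comparison adjusted for Visit 12 CAPS gives 10 − 10ρ = 10(1 − ρ), which is 4, 3 and 2 points in favour of 125 mg at ρ = 0.6, 0.7 and 0.8 (simulated: 3.8, 3.0, 1.9).

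**The case against.** The comparison is optional, labelled exploratory and based on very small groups, and it cannot alter the primary result. Those points stand and limit the importance of the matter. They do not remove a bias whose mechanism is known.

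The documents also do not tie the choice to CAPS, which the independent rater collects; Protocol 2.4 ties titration to session experience. So a reader who infers that the comparison *will* favour 125 mg goes too far. The direction depends on who steps up, and the bias may be nil.

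Three other stronger readings are tempting and are not supported:

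- *The size condition is always met and would allow a comparison against one or two stayers.* Read alone, 'either group' is satisfied by the 125 mg arm. The next sentence of Protocol 12.0 deals separately with fewer than three stayers, so 'either' is most likely loose wording for 'each'. SAP 9.9.3 asks only that group sizes be sufficient.
- *No comparison by randomised arm is planned.* SAP 9.9.2.1 probably is one, since the SAP generally uses the mg labels for Stage 1 assignment. It should say so, because the parallel sentence for the 40 mg crossover subjects concerns a single group and can only be a within-group test.
- *The comparison exists to select the session-3 dose for later trials.* The stated exploratory objective is the effect of the third session. Protocol 5.1.3 links information on optimal dose to subjects' perceptions.

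**Conclusion.** The point holds as a conditional one. Grouping by session-3 dose received is not a randomised comparison, with or without the switchers, and change from Visit 12 exposes it to regression to the mean.

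Under the assumed SD of 25 and half of the 100 mg arm stepping up, the spurious 125 mg advantage with switchers included ranges from about 10/7.5/5 points (strongest selection) through about 4/3/2 (moderate) to nil, at correlations 0.6/0.7/0.8. It reverses if better responders step up. Excluding switchers still leaves about 8/6/4 points at the strongest selection. SD, correlation and choice rule are all assumptions, and the points scale in proportion to the SD. The false-positive rate rises only modestly, so the main harm is a misleading estimate. The primary Visit 12 analysis is unaffected.

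**What to change.** 1. In SAP 9.9.2.1, state that the 100 mg and 125 mg groups are the randomised Stage 1 arms ('100 mg with optional increase' v 125 mg). Make this the only inferential between-dose comparison of Visit 12 to Visit 17 CAPS change, unadjusted.
2. Allow a version adjusted for Visit 12 CAPS only as a sensitivity analysis, with a note that the covariate is a post-randomisation outcome.
3. In Protocol 12.0 and SAP 9.9.3, present stayers and switchers descriptively beside their Visit 12 CAPS, labelled non-randomised and without p-values.
4. If the size condition in Protocol 12.0 is kept, change 'either group' to 'each group' so that it agrees with the sentence after it.

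The cost is wording only: arm, Visit 12 CAPS and session-3 dose are already collected, and the dosing choice itself is left as it is. Two things are given up. There is no formal test of the chosen dose, and if most 100 mg subjects step up, the arm comparison says little about the session-3 dose itself. The comparison by dose received could not have supported a causal reading in either case.
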